Carbamates generally do not accumulate in mammalian tissue and the cholinesterase inhibition reverses rapidly once exposure ceases. Complete recovery from an acute poisoning by bendiocarb, with no long term health effects, is possible if exposure ceases and the patient has time to recover their normal level of cholinesterase before succumbing to symptoms. In non-fatal cases, the illness usually lasts less than 24 hours. Bendiocarb vapors rapidly produce mucous membrane and upper airway irritation and bronchospasm, followed by systemic muscarinic, nicotinic, and central effects if exposed to significant concentrations [39].

Our project will carefully monitor potential exposure to chemicals on our study population. In our Phase II entomological trial utilizing Actellic 300CS, we performed individual acceptability surveys in 160 houses, including 630 individuals ([name] et al. unpublished). Our survey detected 19 cases (3%) of symptoms compatible with a reaction to the insecticide. The most common signs (accounting for 85% of symptoms) were headache, nausea and skin irritation. All of the symptoms reversed within 1-2 days without the need for medical intervention. Our study will treat any signs of intoxication as adverse events and will report them accordingly (see DSMP section). As for insecticide applicators, we will follow WHO recommended practices, which include wearing personal protection equipment and making insecticide dilutions using pre-filled sachets with the right amount for each machine charge (see manual of procedures for detailed steps).

Agricultural use of bendiocarb and pirimiphos-methyl have been associated with risk of environmental contamination[38, 39], as both insecticides are soluble in water and toxic to birds, fish and arthropods. The doses and mode of application in indoor residual spraying are not seen as a source of environmental contamination by WHO, due to difficulty in having insecticides runoff into surface waters. There is a risk of environmental contamination if water used for washing spraying equipment is not properly handled. We will follow Mexico's MOH strict procedures for insecticide preparation, equipment cleaning and insecticide disposal (http://www.cenaprece.salud.gob.mx/programas/interior/vectores/descargas/pdf/guia_rociado_residual_intradomiciliar.pdf).

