Intervention evaluation. The epidemiological impact of TIRS on the primary endpoint will be evaluated by active (enhanced) surveillance to detect and lab-confirmed symptomatic DENV, CHIKV or ZIKV from July 1st to December 31st of each season (the period of peak ABV transmission, Fig 3, and right after TIRS application) (see timeline). As ABV transmission in Merida is highly seasonal, and a single TIRS application covers most of the peak transmission season (Fig 3), focusing active surveillance during a 6-month period after spraying will be more efficient and cost-effective to quantify the epidemiological impact of TIRS than spraying twice and maintaining active surveillance during the period of low transmission. Epidemiological impact will be further assessed in a secondary endpoint using yearly serosurveys performed after the peak transmission season (January-April) to serologically detect interval ABV infections. Entomological impact will be measured by standardized collections of adult and immature *Ae. aegypti* in a sample of houses from each cluster during July 1st-December 31st, coinciding with active surveillance.

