6 STATISTICAL CONSIDERATIONS

6.1 Study Outcome Measures

Outcome measures are summarized in the following table:

Type	Name	Time Frame	Brief Description
Primary	Laboratory-confirmed	Post-treatment	Laboratory-confirmed (virologically [RT-PCR testing of acute samples] or serologically [IgM and IgG ELISA testing of paired acute and convalescent samples]) symptomatic DENV, CHIKV or ZIKV.
Secondary	Laboratory confirmed	Post-treatment	Laboratory confirmed (serologically, [IgG ELISA and neutralization testing of annual surveillance samples]) DENV, CHIKV or ZIKV infection
Secondary	Aedes aegypti infection	Post-treatment	Ae. aegypti mosquito infection rates with DENV, CHIKV, ZIKV (assessed by RT-PCR)
Secondary	Aedes aegypti infestation	Post-treatment	Ae. aegypti indoor entomological indices (adult presence and abundance, female presence and abundance, bloodfed female and abundance)
Secondary	Community acceptance	Post-treatment	Percentage of households receiving the intervention that would recommend it to others in the community (assessed by household surveys)
Secondary	Safety profile	Post-treatment	Percentage of households receiving the intervention that had evidence of a reaction to the insecticide (assessed and confirmed by study doctors)

The primary endpoint will be binary (infected yes/no) and will be used as is for the Cox proportional hazards model. Additional variables will include date of onset of symptoms as well as house and cluster ID. No transformations will be made on such variables.

For secondary endpoints, epidemiological data will also be binary (interval seroconversion, which is the combined assessment of the serological status of a participant between annual serosurveys) and used in logistic models without transformation.

For infection in mosquitoes, we will collect binary data (a mosquito pool is either infected or not), and transform it into minimum infection rates (MIR): $(1/\# \text{ mosquitoes in the pool}) * 1,000$. This measure assumes that, when a pool is positive, it was due to at least one mosquito. That is why it is called 'muminimum'.

For mosquito collections, data will be collected as counts (number per house) and used as is for negative-binomial analysis or used to calculate infestation (binary at the house level, with a house being infested or not). Both measures will be used as described in [34].

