We will perform household surveys to assess the acceptability of the intervention for those households receiving it. We will quantify the % of heads of household that would recommend the intervention to others.

Upon receipt of a sign of potential health reaction to insecticides used, doctors will visit the household and assess whether it could be related to the application. The % of households reporting signs of potential intoxication will be quantified for houses receiving the intervention.

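### Section 6.1 counts insecticide reactions only after a sign is received and describes no scheduled symptom question, so the household rate risks missing mild reactions and cannot be compared directly with the pilot's per-person 3%

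*Combined protocol and SAP*

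**What the plan says.** All references are to the combined protocol and SAP.

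- **How reactions are found (6.1, text after the outcome table).** "Upon receipt of a sign of potential health reaction to insecticides used, doctors will visit the household". The doctor then judges whether the sign could be related to the spraying. The text does not say who supplies the sign, or how soon the visit follows.
- **What is counted (6.1).** The text says: "The % of households reporting signs of potential intoxication will be quantified for houses receiving the intervention". The outcome table defines the same endpoint as "Percentage of households receiving the intervention that had evidence of a reaction to the insecticide (assessed and confirmed by study doctors"). One numerator is households that report; the other is households with a doctor-confirmed reaction.
- **The household survey (6.1).** "We will perform household surveys to assess the acceptability of the intervention for those households receiving it". The one output named is the share of household heads who would recommend TIRS. The table likewise ties surveys to acceptance and doctors' assessment to safety.
- **The pilot (1.3.1).** "we performed individual acceptability surveys in 160 houses, including 630 individuals". "Our survey detected 19 cases (3%) of symptoms compatible with a reaction to the insecticide". Headache, nausea and skin irritation made up 85% of symptoms. "All of the symptoms reversed within 1-2 days without the need for medical intervention".
- **Deferred detail (1.3.1).** Signs of intoxication are to be handled as adverse events, with a pointer to the Data Safety and Monitoring Plan. That plan, its forms and the Manual of Procedures are appendices outside the reviewed text.

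**The concern.** The pilot's reactions were mild, brief and needed no care. The sponsor learned of them by surveying people. Section 6.1 describes the opposite approach for the trial: ascertainment starts when a sign arrives. A headache or skin irritation that lasts a day or two may never be reported, or may be over before a doctor can confirm it. Missed reports can only lower the rate.

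The unit also changes. The pilot's 3% is a share of people, and the trial's endpoint is a share of houses. A reader who sets one beside the other compares different quantities found by different methods.

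Section 1.3.1 names intoxication as the most sensitive risk of the study. If reactions are counted only when reported, a low percentage could mean few reactions or few reports, and the trial's data could not tell these apart.

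**Working it through.** **1. Reproduce the pilot figure.** Inputs from 1.3.1: 19 cases, 630 individuals, 160 houses.

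19/630 = 0.0302, or 3.0% (exact 95% CI 1.83% to 4.67%). This agrees with the stated 3%.

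**2. Convert it to the trial's unit.** Mean surveyed persons per house: 630/160 = 3.94. How the 19 cases were spread over houses is not given, so I take three cases:

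- Cases fill whole houses of average size: 19/3.94 = 4.8, rounded up to 5 houses; 5/160 = 3.1%.
- Cases are independent within houses: 1 - (1 - 0.0302)^3.94 = 11.4%.
- Every case is in a different house: 19/160 = 11.9%.

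With the pilot's solicited method, the household rate would be about 3.1% to 11.9%.

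**3. Effect of incomplete reporting.** Let s be the share of affected houses that are reported and counted. The documents give no value for s, so the values below are assumptions. Recorded rate = s x household rate.

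| Assumed s | Maximal clustering | Independence | One case per house |
|---|---|---|---|
| 1.00 | 3.1% | 11.4% | 11.9% |
| 0.75 | 2.3% | 8.5% | 8.9% |
| 0.50 | 1.6% | 5.7% | 5.9% |
| 0.25 | 0.8% | 2.8% | 3.0% |
| 0.10 | 0.3% | 1.1% | 1.2% |

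The value of s at which the recorded household rate equals the pilot's 3.02%: 3.02/3.125 = 0.97 under maximal clustering, 3.02/11.36 = 0.27 under independence, and 3.02/11.875 = 0.25 with one case per house.

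**4. Could other scheduled contacts fill the gap?** Section 3 plans weekly visits and twice-weekly calls. These cover enrolled children and look for Aedes-borne illness, as part of "active (enhanced) surveillance to detect and lab-confirmed symptomatic DENV, CHIKV or ZIKV from July 1st to December 31st".

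- Houses in the 25 TIRS clusters: section 3 equates 10% of central houses with 1,350, so there are 13,500 in 50 clusters and 6,750 in the TIRS arm. Scaling from 9 to 25 blocks at equal density: 6,750 x 25/9 = 18,750.
- Enrolled children in the TIRS arm: 25 x 92 = 2,300.
- Houses with an enrolled child: at most 2,300/18,750 = 12% at full coverage, or 16% to 20% if coverage is assumed to be 75% to 60%. Section 5.1 gives about 1,600 houses instead of 1,350. Scaled in the same way, the range is 10% to 17%.

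Timing is less clear. Section 6.4 has spraying finished before July 1 of the first season. The timeline text in section 3 says June-July, and the start dates and durations in sections 3 and 5.1 also allow some spraying in July. The passages need reconciling. Some overlap with the visits is possible, but the population and purpose of the visits still do not match.

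**The case against.** The strongest reply is that section 6.1 is a summary. Section 1.3.1 promises careful monitoring and points to the Data Safety and Monitoring Plan, where follow-up after spraying would normally be set out. That plan was not available, so solicited follow-up may exist. The sign in 6.1 has no named source: spray supervisors, nurses or the survey could supply it. Section 3 also describes a toll-free line, open at all hours, to an on-call physician for any symptom in the family. The pilot's reactions came from acceptability surveys, and the trial plans acceptability surveys too, so the same instrument may be intended.

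This stands to a large extent. A reader might infer that the endpoint rests solely on families' spontaneous reports and that the trial is bound to understate the rate. The documents support neither statement. What remains is that 6.1 defines the endpoint, links the survey to acceptance only, and neither describes nor cites any solicited question. The hotline depends on the family calling.

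The second reply is that doctor-confirmed reactions are a legitimate and more specific endpoint. Solicited headache or nausea, with no survey of control houses, would include background symptoms. Questioning everyone in all treated houses would mean about 18,750 x 3.94 = 74,000 people per season. This is right, and it is why the solicited rate should stand beside the doctor-assessed one and be limited to the houses the survey covers.

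**Conclusion.** The concern holds as a risk. Following section 6.1 as written, mild reactions of the kind seen in the pilot may be missed, and any error from missed reports is downward. Its size cannot be computed, because the documents give no reporting fraction; the table of assumed values shows the dependence and is not an estimate.

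The trial's household percentage cannot be compared directly with the pilot's per-person 3%, which corresponds to about 3.1% to 11.9% of households. This range rests on the average house size in the pilot survey and on unknown clustering of cases.

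A reader might also infer that the trial's figure would look better than the pilot's 3% through method alone. That does not follow. With cases spread over houses, the household rate falls below 3% only if fewer than about 25-27% of affected houses are counted, so it could exceed 3% despite substantial under-reporting.

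The endpoint is a descriptive secondary percentage with no test, and the primary analysis is unaffected. This is a cheap improvement.

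**What to change.** In section 6.1:

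1. Add the pilot's individual symptom questions (each household member, onset relative to the spray date) to the acceptability survey already planned for treated houses. Ask them soon after spraying, in whatever houses that survey covers.
2. Report the solicited per-person and per-house rates beside the doctor-assessed endpoint, not in place of it. The per-person rate can then be set against the pilot's 3%.
3. State how and when signs are sought and from whom, and cross-reference any solicited follow-up in the Data Safety and Monitoring Plan. If that plan already asks about symptoms after spraying, the cross-reference may be enough in place of new questions.
4. Reconcile the two numerators, households that report and households with a doctor-confirmed reaction, or report both under separate names.

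The cost is a few questions and a paragraph of text, with no additional houses. Interviews become slightly longer. The solicited rate will include background symptoms because control houses are not surveyed, and the report should say so.

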6.2 Sample Size Considerations

The size of clusters for the intervention will be 5x5 city blocks. This extent was chosen because: a) the area is large enough to contain more than the 92 age-eligible children required for the epidemiological evaluation; b) *Ae. aegypti* dispersal is limited, rarely exceeding 100m[58], thus concentrating our evaluation in the center of the cluster will provide a less biased estimate of intervention efficacy; c) prospective mobility surveys informing how human mobility may affect the placement of clusters. Surveys performed on 800 FSD residents showed that FSD cohort participants living in Merida had about 60% their mobility occurring within 1km of the house (Fig 7).

Given the large extent of movement, separating clusters by distance (e.g., larger than 1 km separation) would be unfeasible. Instead, our approach for the trial was to focus on a “fried egg” design, where entomology and epidemiological follow-up of study participants will occur within the central 3x3 city blocks of the 5x5 city-block cluster (Fig 8).

Randomization:

The study area includes 286 hot-spot census tracts, 192 of which have total population size of at least 1,000, per the 2010 census. Census tracts are categorized into four sectors. For each census tract, we have characterized the following features that are used as balancing factors:

- Population size, per 2010 census.
- Population density, per 2010 census.
- Percent employed population, per 2010 census.
- Cumulative number of ABD cases between 2008 and 2016 (per passive surveillance).

[figure not shown]

Fig. 7. Probability of moving a given distance from the home (y-axis) as a function of the distance from home (x-axis) for Merida residents, and stratified by age group ([name] et al. unpublished).

Fig. 8. Structure of a study cluster. Yellow areas will receive TIRS, whereas blue areas will receive TIRS and participate in the epidemiological and entomological evaluation of the intervention.

We simulated 1,000,000+ random allocation patterns (25 clusters in group A, 25 clusters in group B – allocation to TIRS/routine vector control determined later), and we use covariate-constrained randomization[41] to eliminate the allocation patterns with an imbalance of $\pm 10\%$ on any of the continuous balancing factors listed above. Specifically, for each balancing factor, if for a given allocation pattern, the mean of group A divided by the mean of group B was greater

than 1.1 or less than 1/1.1, that pattern would not be considered for potential selection. Furthermore, we eliminate any allocation pattern with imbalance in the number of clusters per arm per sector greater than ± 1 . We will implement checks to satisfy the criteria that the design is not overly constrained, as proposed by Moulton[41] (e.g. pairs of clusters always or never appearing in the same arm). For each retained allocation patterns, we calculate the mean distance from the centroid of each cluster to the centroid of its nearest neighbor also in the trial. We restrict to the top 10% of allocation patterns with the largest mean distance. Preliminary exercises returned over 1,500 allocation patterns satisfying all selection criteria. Sample allocation patterns are plotted in Fig 9.

Given the set of allocation patterns that meet the above balancing criteria, we will use equal probability sampling to randomly select one allocation. For participant enrollment, the study teams will be provided with a list of 50 census tracts for inclusion in the study, without record of which census tracts are in Group A or B. At this time, households and individuals will be invited to participate in the study. No participant or investigator will have knowledge of their allocation. **After completing the enrollment process, we will then use a random number generator to determine which group (A or B) is allocated to TIRS, where each group has a 50% probability.**

Power and sample size

To assess power and sample size requirements, we analyzed historical passive surveillance data from the 192 hot-spot census tracts with population size of at least 1,000 (from our publication characterizing the ABV hot-spot area [40]). We use yearly data from 2008 to 2016 on the number of dengue, chikungunya, and Zika cases recorded in children 0-14 years each year by census tract[40]. Data were combined into pairs of adjacent years to mimic a two-year trial period. The table below summarizes the mean incidence (number of cases over two-year period/number of children) and intracluster correlation coefficient (ICC) for a given two-year period.

Data source	Mean	ICC
2008+2009 Dengue	0.0402	0.0345
2009+2010 Dengue	0.0530	0.0289
2010+2011 Dengue	0.0572	0.0164
2011+2012 Dengue	0.0847	0.0153
2012+2013 Dengue	0.0729	0.0188

[figure not shown]

Fig 9. Two examples of outputs from the constrained randomization into two groups.

2013+2014 Dengue	0.0455	0.0256
2014+2015 Dengue/Chik	0.0581	0.0229
2015+2016 Any	0.0385	0.0151

For our sample size calculations, we conservatively assume a low incidence (4% over a two-year period) and high ICC (0.035). Sample size is shown below for 50 clusters, considering 80% power and 90% power and TIRS efficacy from 70 to 90%. Sample sizes are adjusted for the study design effect and expected 20% loss to follow-up (LTFU).

POWER	TIRS EFFICACY	NUMBER OF EVENTS	TOTAL EFFECTIVE SAMPLE SIZE	NUMBER PER CLUSTER, UNADJUSTED	NUMBER PER CLUSTER, ADJUSTED FOR LTFU	TOTAL SAMPLE SIZE, ADJUSTED FOR LTFU
90%	70%	38	1390	>500		
	75%	30	1164	122	152	7600
	80%	24	984	62	77	3850
	90%	16	714	28	35	1750
80%	70%	28	1038	74	92	4600
	75%	22	870	43	54	2700
	80%	18	734	30	37	1850
	90%	12	534	17	21	1050

Assuming 4% incidence over a two-year period, 70% TIRS efficacy, an ICC of 0.035, and 20% loss to follow-up, we will require 92 age-eligible children enrolled per cluster for an overall sample size of 50 clusters and 4,600 children to have 80% power to detect a significant reduction in ABV incidence with TIRS.

Figure 10 below summarizes the distribution of the number of children less than or equal to 14 years of age in each cluster, based on the 2010 census. The minimum size is 145 children. The median is 546 children.

[figure not shown]

Figure 10. Distribution of children aged 0-14 per cluster, based on 2010 census.

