3 STUDY DESIGN

We will pursue a two-arm CRCT with a total of 50 clusters of 5x5 city blocks each, including at least 92 enrolled age-eligible participants per cluster, with 25 clusters randomly allocated to receive TIRS and 25 clusters not receiving TIRS (Fig 5) (see section 4.4 in the Clinical Trial Protocol). A total of 4,600 age-eligible individuals will be recruited for the trial. This sample size accounts for a 20% loss to follow-up. Routine MOH vector control actions (primarily, truck-mounted ULV spraying of chlorpyrifos, larvicide with altosid® and indoor space spraying in premises of suspected ABV cases) performed in response to symptomatic ABV cases reported to the healthcare system will not be interrupted and could occur across both study arms. Therefore, our trial will compare TIRS to routine ABV prevention and control, providing an opportunity to quantify intervention efficacy and potential benefits in comparison to existing practice. Clusters will be located within the areas identified as hot-spots of ABV transmission[40] (Fig. 5). Placing all clusters within the zone of high ABV incidence will increase power by focusing on an area with higher event rates and lead to a more homogeneous design (e.g., less likely to have imbalance across trial arms). We will use a covariate-constrained randomization strategy[41] to randomly select 50 clusters from the set of census tracts in the hot-spot region. This approach ensures that key cluster-level variables (e.g., historical ABV transmission, population size and density, % employed population) are not more than 10% different between trial arms and maximizes the distance between neighboring clusters. To further reduce contamination and edge effects, while all households in TIRS clusters will be offered the intervention, epidemiological and entomological evaluation will occur in the center of each cluster, following a “fried egg” design (blue blocks in inset of Fig. 5). Enrollment into the trial will occur in all clusters before TIRS allocation has been determined, in order to prevent selection bias.

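### Historical case counts and population are each balanced to 10%, but incidence is not, so the arms' historical ABV risk is not guaranteed to lie within 10%

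*Combined protocol and SAP*

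**What the plan says.** Section 6.2 (Randomization) describes the pool: "The study area includes 286 hot-spot census tracts, 192 of which have total population size of at least 1,000, per the 2010 census". The balancing factors are "Population size, per 2010 census", population density, percent employed, and "Cumulative number of ABD cases between 2008 and 2016 (per passive surveillance". The last is a count with no denominator and no stated age range.

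The enumeration is described thus: "We simulated 1,000,000+ random allocation patterns (25 clusters in group A, 25 clusters in group B". Each factor is tested on its own through the ratio of the two arm means, and patterns with a ratio above 1.1 or below 1/1.1 are discarded. Two more filters follow: at most one cluster of imbalance per sector, and only the 10% of patterns with the largest mean nearest-neighbour distance. Preliminary runs left over 1,500 patterns. One is drawn with equal probability, and after enrolment a 50:50 draw decides which group receives TIRS.

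Section 3 says of the key cluster-level variables: "e.g., historical ABV transmission, population size and density, % employed population) are not more than 10% different between trial arms".

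The power part of Section 6.2 uses yearly 2008–2016 case data in children aged 0–14 for the same 192 tracts and tabulates "the mean incidence (number of cases over two-year period/number of children". That rate is not a balancing factor.

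Section 3 sets at least 92 enrolled children per cluster and 4,600 in all (50 × 92). The primary Cox model in Section 6.4 names no adjustment covariates. The example covariates for the secondary adjusted model do not include historical incidence.

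**The concern.** Enrolment is planned at about 92 children per cluster whatever the size of the tract. The numbers available do vary: Section 6.2 gives a minimum of 145 and a median of 546 children aged 0–14 per cluster. A cluster's expected number of endpoints therefore follows its rate, not the number of cases its tract recorded. A raw count mixes rate with population. Balancing population as well helps, but two separate limits of 1.1 do not make one limit of 1.1 on their quotient.

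Historical transmission is the balancing factor most directly tied to the primary endpoint. With 25 clusters per arm and an unadjusted primary model, an imbalance in risk left in the one pattern drawn moves the estimated hazard ratio up or down.

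**Working it through.** **1. The plan's own figures.** The 92 per cluster reproduces for 80% power and 70% efficacy:
- Freedman events: (1.960 + 0.842)² × (1.30/0.70)² = 27.07, rounded up to an even 28.
- Event probabilities: 0.04 in controls and 1 − 0.96^0.30 = 0.0122 under TIRS; mean 0.02609. Effective size: 27.07/0.02609 = 1,038.
- Per cluster: 1,038 × 0.965/(50 − 1,038 × 0.035) = 73.3, so 74. Then 74/0.8 = 92.5, printed as 92.

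This is one figure for every cluster, not scaled to tract size. The count of over 1,500 retained patterns cannot be reproduced without tract data. If exactly 1,000,000 patterns were drawn, it implies 1,500/0.10 = 15,000, or 1.5%, passing the balance and sector rules.

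**2. Bound on pooled incidence.** Pooled incidence in an arm is mean cases divided by mean population. The between-arm ratio is (case ratio)/(population ratio). With each in [1/1.1, 1.1], the largest value is 1.1/(1/1.1) = 1.21.

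**3. Mean tract rate.** With equal enrolment, an arm's expected endpoints are proportional to 92 × 25 × r̄, where r̄ is the plain mean of the tract rates. For tract population n and rate r, mean cases = n̄ · r̄ + cov(n, r), so r̄ = (mean cases)/n̄ − cov(n, r)/n̄. The rule restricts mean cases and n̄ but not the within-arm covariance. Hence 1.21 does not cap the ratio of r̄.

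**4. Spread of historical incidence.** From the plan's table, CV = √(ICC(1 − p)/p) for one two-year period:
- 2011+2012: √(0.0153 × 0.9153/0.0847) = 0.41.
- 2008+2009: √(0.0345 × 0.9598/0.0402) = 0.91.

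The balancing factor is cumulative, so I combined the four non-overlapping pairs (2008+09, 2010+11, 2012+13, 2014+15). Their means sum to 0.0402 + 0.0572 + 0.0729 + 0.0581 = 0.2284. Their between-tract SDs, √(ICC · p(1 − p)), are 0.0365, 0.0297, 0.0356 and 0.0354.
- Tract effects independent over time: 0.0688/0.2284 = 0.30.
- Perfectly correlated: 0.137/0.2284 = 0.60.

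**5. Simulation.** 192 tracts, 50 drawn, 25 against 25, all four factors held to the 1.1 rule. Assumptions, because the documents give no tract-level values: population CV 0.2–0.5 with a minimum of 1,000; cumulative incidence CV 0.30–0.60; density CV 0.2–0.4; percent-employed CV 0.1; population–risk correlation −0.3 to +0.3; Poisson counts. The sector rule and distance cut were used only to estimate yield. Three of the scenarios:

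| Density CV / population CV / incidence CV / correlation | Yield per million | Pooled ratio above 1.1 | Mean-rate ratio above 1.1 | 95th percentile, mean-rate ratio |
|---|---|---|---|---|
| 0.4 / 0.2 / 0.3 / +0.3 | 1,593 | 7.1% | 7.9% | 1.11 |
| 0.2 / 0.35 / 0.45 / −0.3 | 1,557 | 18.9% | 20.8% | 1.16 |
| 0.4 / 0.5 / 0.6 / −0.3 | 619 | 21.5% | 29.8% | 1.19 |

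Over the whole grid, 7–22% of accepted patterns exceed 1.1 on pooled incidence and 8–30% on the mean tract rate. In scenarios yielding at least 1,500 per million, as the plan reports, the shares are 7–19% and 8–21%. A separate run with population CV of about 0.4–0.7 gave up to about 36%, with a 95th percentile of 1.13–1.23, but its yields fell below the plan's. With no constraint at all, 28–58% would exceed 1.1.

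**6. Effect on the estimate.** If trial risk is proportional to historical risk, a 10% imbalance turns a true hazard ratio of 0.30 into 0.30/1.1 = 0.27 or 0.30 × 1.1 = 0.33 (efficacy 73% or 67%). The pooled maximum of 1.21 gives 0.25 or 0.36.

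**The case against.** The existing rules already do much of the work. Population is balanced alongside the count, which limits pooled incidence to 1.21 and leaves most accepted patterns within 10%. If historical ABV transmission in Section 3 simply means the case count, that sentence is true as written. The 50:50 draw between groups A and B means neither arm is favoured in advance. The sample size uses an ICC of 0.035, slightly above the highest tabulated value, and takes no credit for constrained randomisation; the primary variance estimator allows for clustering. Past passive-surveillance rates are also only a proxy for risk during the trial.

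All of this stands, and it limits the size of the point. It does not remove it: one pattern is drawn and analysed, the plan constrains randomisation precisely to avoid chance imbalance in risk, and it already holds a better variable than the one it balances.

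Three stronger readings are tempting and not supported:
- **Most accepted patterns are imbalanced, or differ by 20%.** Shares near a half require a CV of about 0.9, which comes from a single two-year pair, not a nine-year total. With a CV of 0.3–0.6, at most about 8% of accepted patterns exceed 20%.
- **The efficacy estimate is biased.** The coin flip rules out systematic bias.
- **The count covers all ages.** Section 6.2 states no age range for it.

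**Conclusion.** The point holds in a limited form. Balancing count and population separately does not hold historical incidence within 10%: the pooled ratio can reach 1.21, and the rule sets no limit on the ratio of mean tract rates. The statement in Section 3 is therefore not guaranteed on the scale that matters with equal enrolment per cluster.

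A minority of accepted patterns is affected: roughly 1 in 12 to 1 in 3, nearer the low end if matched to the reported yield, with a 95th-percentile ratio of about 1.11–1.23. These figures rest on assumed population CVs of 0.2–0.7, a cumulative incidence CV of 0.3–0.6 derived from the plan's means and ICCs, and simplified sectors and geography. The bound of 1.21 needs none of these assumptions.

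The consequence is avoidable chance imbalance, small against a 70% effect. The shift to 0.27–0.33 is an upper bound for a 10% imbalance, because it takes trial risk as proportional to historical risk. The point is worth acting on because the remedy is nearly free.

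**What to change.** Before the pattern is drawn, replace the case count in Section 6.2 with cumulative 2008–2016 incidence per tract: cases in children aged 0–14 divided by children, from the data already used for the power section. Apply the same 1/1.1 to 1.1 rule to the arm means of the tract rates. Then re-run the enumeration and the over-constraint check already planned, and word Section 3 to match. Adding incidence and keeping the count is also acceptable.

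Either way, no accepted pattern can exceed 10% on historical incidence, by construction. In the simulations, replacing the count left the number of acceptable patterns about unchanged or somewhat higher (0.96–1.27 times). Adding incidence kept about 70–92% of them, or about 1,050–1,380 of 1,500. The cost is one line in the randomisation program and a re-run, with no new data, staff or children.

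The sponsor can replace the assumptions above with fact by computing the incidence ratio for each of the patterns already retained.
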